6. GENERAL ANALYSIS DEFINITIONS

6.1 TREATMENT(S)

For the definition of treatment administered during the trial, see section 4 of CTP.

Note: the last day of each of the following periods is excluded from the respective period. It defines the first day of the subsequent period.

- Screening: from informed consent to randomisation
- Post-randomisation (optional^[a]): from randomisation to first trial drug intake in treatment period.
- Treatment period: from first trial drug intake (or re-start of treatment if interruption) to last trial drug intake (or the day before start date of interruption if interruption) plus one day
- Off-treatment (optional^[a]): from start date of interruption to re-start of treatment
- Residual effect period(^[b]): from the last trial drug intake plus one day to last trial drug intake plus 28 days plus one day or to date of first trial drug intake in extension trial, whichever occurs earlier
- Follow-up (optional^{[a][b]}): from last trial drug intake plus 29 days up to the beginning of post-study period. This period is only created if last trial drug intake took place more than 28 days before trial completion, or for patients having prematurely discontinued the treatment and still continuing the trial
- Post-study(optional^{[a][b]}): from the latest between last trial drug intake plus 29 days, 'date of trial completion' (from the trial completion part of the eCRF) plus one day, and 'date of Informed Consent in extension trial' (if applicable). This period is not created if date of first trial drug intake in extension trial is before last trial drug intake plus 28 days

[a] This period is optional insofar as it does not necessarily exist for all patients.

[b] In addition, a residual effect period of 7 days will be used for adverse event analyses to more closely reflect the period of time after the last trial drug intake when measurable drug levels or pharmacodynamics effects are still likely to be present.

As a summary:

- For efficacy analyses, data from randomisation date up to week 52 data will be considered (please see [Section 7.4](#), [Section 7.5](#) and [Section 7.6](#)). For efficacy descriptive analyses over the whole trial period, all data collected after randomisation date will be considered.

- For safety analyses, data from the treatment period, possible off-treatment periods and residual effect period will be considered as on-treatment.

Safety survival analysis over 52 weeks ^[2]	Time to - first dose reduction - first treatment interruption - premature treatment discontinuation	Date of first trial drug intake	- If last drug intake < Day 373: Last drug intake - Else, if last drug intake ≥ Day 373: Day 373
On-treatment safety analyses over 52 weeks	- Adverse events - Laboratory data - Vital signs	Date of first trial drug intake	- If last drug intake < Day 373: Last drug intake + 28 days - Else, if last drug intake ≥ Day 373: Day 373
On-treatment safety analyses (over the whole trial)	- Adverse events - Laboratory data - Vital signs	Date of first trial drug intake	Last trial drug intake + 28 days Off-treatment periods not excluded. However, for safety listings, anything happening during a treatment interruption will be flagged as occurring during the off-treatment period

[1] End date is included. End date will always be checked against the date of first trial drug intake in 1199.225. For safety endpoints, if date of first trial drug intake in 1199.225 is earlier than end date calculated as mentioned in this table, then the end date of the studied period will be substituted by the date of first trial drug intake in 1199.225

[2] For time-to-event endpoint, if a patient does not have an event during the studied period then ■ will be censored on the day corresponding to the end date of the studied period

6.2 IMPORTANT PROTOCOL VIOLATIONS

The following table defines the different categories of important PVs (7). As there is no Per Protocol Set planned in this trial, none of the IPVs will lead to exclusion from a patient set. However the proportion of patients with IPVs will be presented for completeness purposes and to demonstrate the adherence to the CTP.

Unless otherwise specified, the following IPVs in Table 6.2: 1 have been defined over 52 weeks as this is the primary timepoint of interest in this trial. IPVs detected over the whole trial period will be reported in Section 16.1.13.1 of the CTR and the derivation will be adapted accordingly.

Table 6.2: 1 Important protocol violations over 52 weeks

Category/Code	Description	Requirements	Excluded from
A	Entrance Criteria Not Met		
A1	Inclusion criteria not met		
A1.1	Patient aged <18 years when signing his/her informed consent	Inclusion criteria 2 not met (Age <18 at the date of Informed Consent – Or other age restriction specified as per a local amendment) Automatic IPV	None
A1.2	2013 ACR / EULAR classification criteria for SSc not fulfilled OR no chest HRCT performed demonstrating SSc related Interstitial Lung Disease pattern or extent of fibrotic disease in the lung <10% on HRCT	Inclusion criteria 3 or 5 not met; or extent of fibrotic disease <10% according to database Automatic IPV	None
A1.3	SSc disease onset (defined by first non-Raynaud symptom) > 7 years of Visit 1.	CRF date of onset (defined by first non-Raynaud symptom) > 7 years before date of Visit 1, according to database Automatic IPV	None
A1.4	FVC < 40% of predicted value at Visit 2	FVC < 35% (5% tolerance) at visit 2 according to database Automatic IPV	None
A1.5	Single breath DL _{CO} (corrected for Hb) < 30% of predicted value at Visit 2	DLCO <25% (5% tolerance) at visit 2 according to database Automatic IPV	None
A2	Exclusion criteria met		
A2.1	Patient has laboratory values that indicate additional risk at Visit 1: a) >1.5xULN for AST or ALT b) >1.5xULN for Bilirubin c) Creatinine clearance < 30 mL/min (Cockcroft-Gault formula)	Laboratory values out of range at visit 1 according to the database Automatic IPV	None

Table 6.2: 1 Important protocol violations over 52 weeks (cont'd)

Category/Code	Description	Requirements	Excluded from
A2.2	Patient with other disease(s) which are excluded as per exclusion criteria	Exclusion criteria 6-7-8-9-10-11-12-13-14-20-25-26 met Automatic IPV	None
A2.3	Forbidden previous therapy	Exclusion criteria 15-16-17-18-19 met Manual IPV based on exclusion criteria and / or to be identified at the site level on the manual PV log / issue log	None
A2.4	Potential risk related to fetotoxicity	Exclusion criteria 21-22 met Automatic IPV	None
B	Informed Consent		
B1	Informed consent not given	Inclusion criteria 1 not met Automatic IPV	None
B2	Informed consent given too late	CRF date of informed consent is after date of Visit 1. Signature of the wrong IC version, and later signature of the correct one will also be part of this IPV category Manual IPV / issue log	None
B3	Informed consent not given or withdrawn for one of the substudies (HRCT, Skin Biopsy) but procedure done	To be identified at the site level on the manual PV log/ issue log	None
C	Trial medication and randomisation		
C1	Incorrect trial medication taken	Medication kit taken (between Baseline - excluded - and Week 52) which does not match the treatment which the patient was randomised to (to be determined after unblinding). Review of MORM listings and / or to be identified at the site level on the manual PV log / issue log	None
C2	Randomisation not followed	Wrong stratification factor at time of randomisation. OR Wrong medication kit given leading to the patient taking treatment different from the one randomised by IXRS at time of randomisation (Visit 2). This is an IPV only if the medication error leads to an actual treatment switch (to be determined after unblinding). Review of MORM listings and / or to be identified at the site level on the manual PV log/ issue log	None

Table 6.2: 1 Important protocol violations over 52 weeks (cont'd)

Category/Code	Description	Requirements	Excluded from
C3	Overall Compliance (between baseline and Week 52) not between 80% and 120% inclusive (or non-compliance based on investigator assessment)	In case calculated overall between baseline and Week 52 compliance is missing: If the answer to the question "Did the patient take trial medication as instructed?" of the CRF is "No" at at least one of the visits where the compliance cannot be calculated, then an IPV will be flagged. Otherwise no IPV although calculated overall compliance between baseline and Week 52 is missing. Automatic IPV with review of MQRM listings	None
C4	Trial medication not interrupted when ALT or AST \geq 5 fold ULN	Based on liver enzyme elevation and interruptions reported between baseline and Week 52 Automatic IPV	None
C5	Trial medication not permanently discontinued after signs of liver enzyme elevations were observed that a) are indicative of hepatic injury as defined in Section 5.3.7.1 of the CTP b) correspond to ALT or AST \geq 3 fold ULN despite dose reduction or treatment interruption for 2 weeks or more	All patients where signs of liver enzyme elevations (between baseline and Week 52) are not dealt with according to the requirements of the CTP. Manual IPV based on review of MQRM listings	None
C6	Medication code broken inappropriately	Reason for medication code broken is inappropriate (e.g. not emergency) and data collected after unblinding between baseline and Week 52 Review of MQRM listings and / or to be identified at the site level on the manual PV log / issue log.	None
D	Concomitant Medication		
D1	Patient received prohibited concomitant therapies between baseline and Week 52 (see Section 4.2.2.1 of the CTP)	Based on concomitant therapies reported between baseline and Week 52 Review of MQRM listings and / or to be identified at the site level on the manual PV log / issue log	None

Table 6.2: 1 Important protocol violations over 52 weeks (cont'd)

Category/Code	Description	Requirements	Excluded from
E	Missing data		
E1	Patient without any physical assessment for more than 6 months, although under study medication	Missing results for physical assessment for more than 6 months during the trial Automatic IPV	None
E2	No baseline or post-baseline FVC assessments up to Week 52	Automatic IPV	None
E3	No baseline or post-baseline mRSS up to Week 52	Automatic IPV	None
E4	No reliable ^[1] baseline or post-baseline SGRQ total score up to Week 52 ^[1] As per exclusion criteria 24	No baseline or post-baseline value or exclusion criteria 24 met Automatic IPV	None

Automatic PVs are those detected via an automated programming process using SAS.

Note: IPV's E2, E3 and E4 will be not be reported over the whole trial period.

A summary of IPV decisions will be provided in the final BRPM minutes.

6.3 PATIENT SETS ANALYSED

- Screened set
This patient set includes all patients having signed informed consent and performed visit 1.
- Randomised set (RS)
This patient set includes all randomised patients, whether treated or not.
- Treated set (TS)
This patient set includes all randomised patients who received at least one dose of trial medication.
- PK set (PKS)
This patient set includes those in the Treated Set with at least one valid plasma concentration available

6.4 SUBGROUPS

The subgroups listed in [Table 6.4: 1](#) will be investigated. Selected variables as defined in [Section 5.4](#) will be used to characterize the study population in all subgroups. Selected safety analyses as well as efficacy analyses on the primary and both key secondary endpoints will be done on some selected subgroups only (only in subgroups with more than 20 patients over both treatment groups within each category of the subgroup)

For more details on the planned analysis, please refer to [Section 7.4.3](#).

Table 6.4: 1 Subgroup analyses – List of subgroups

	Description of study population ^[1]	Efficacy analyses on the primary and both key secondary endpoints ^[2]	Safety analyses ^[3]	Rationale for subgroup analysis
ATA status (Positive / Negative)	X	X	X	ATA is the stratification factor for randomisation in the trial
Gender (Male / Female)	X	X	X	SSc differences in males vs females have been described (Clin Exp Rheumatol. 2017 Sep-Oct;35 Suppl 106(4):89-97)
Age (<65 / ≥65)	X	X	X	Regulatory requirement
Race (White / Asian / Black or African American) ^[4]	X	X	X	Regulatory requirement
Region (Asia / Europe / Canada and United States / Rest of the World)	X	X	X	Assessing the homogeneity of treatment effect across region
Mycophenolate mofetil /sodium use at baseline (Yes / No)	X	X	X	Evaluation of influence of effect of stable background immunosuppressive therapy to study treatment as allowed per CTP
Methotrexate use at baseline (Yes / No)	X			Evaluation of influence of effect of stable background immunosuppressive therapy to study treatment as allowed per CTP
SSc subtype (Diffuse cutaneous SSc / Limited cutaneous SSc)	X	X	X	Evaluation of efficacy and safety in different SSc subtypes as manifestation and course of disease is described as being significantly different

Table 6.4: 1 Subgroup analyses – List of subgroups (cont’d)

	Description of study population ^[1]	Efficacy analyses on the primary and both key secondary endpoints ^[2]	Safety analyses ^[3]	Rationale for subgroup analysis
Baseline bodyweight (≤65kg, >65kg)	X		X	Based upon safety profile of Nintedanib- “Patients with low body weight (< 65 kg), Asian and female patients have a higher risk of elevations in liver enzymes.”

[1] [2] [3] For more details, please refer to [Table 7.4.3:1](#)

[4] Only single race respondents are taken into account. In case more than 20% of patients ticked multiple races in the CRF, then a category “Multiple or missing” will be added for subgroup analyses by race

In addition, US / non-US subgroup analyses will also be done and will be included in Section 16.1.13.1 (efficacy and safety analyses).

6.5 POOLING OF CENTRES

This section is not applicable because centre/country is not included in the statistical model.

6.6 HANDLING OF MISSING DATA AND OUTLIERS

Missing data will not be imputed, except for some sensitivity analyses on the primary and key secondary endpoints.

6.6.1 Primary endpoint

The statistical model used for primary analysis (see [Section 7.4.1](#)) allows for missing data, assuming they are missing at random. Even patients with only one post-baseline assessment can be included in the model and can therefore participate in variance estimation. The statistical model assumes that patients who dropout would have behaved similarly to those who remained in the study.

Several sensitivity analyses will be conducted to investigate the potential effect of missing data on the results of the primary analysis (see [Section 7.4.2](#)).

6.6.2 Secondary endpoints

6.6.2.1 Change from baseline endpoints

The statistical model Mixed effect Model for Repeated Measures (MMRM) used for the analysis of continuous secondary endpoints allows for missing data, assuming they are missing at random.

For the two key secondary endpoints, several sensitivity analyses will be conducted to investigate the potential effect of missing data on the results of the main analysis.

6.6.2.1.1 Modified Rodnan Skin Score

In case of missing score for an area, mRSS total score will be missing.

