5.2.2 Assessment of mRSS

The modified Rodnan Skin Score (mRSS) consists of an evaluation of patient's skin thickness rated by clinical palpation using a 0–3 scale (0=normal skin; 1=mild thickness; 2=moderate thickness; 3=severe thickness with inability to pinch the skin into a fold) for each of 17 surface anatomic areas of the body: face, anterior chest, abdomen, (right and left separately) fingers, forearms, upper arms, thighs, lower legs, dorsum of hands and feet. These individual values are added and the sum is defined as the total skin score (R15-1205).

Further instructions regarding mRSS assessment will be provided in the ISF.

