5.2.1 Key secondary endpoint(s)

- Absolute change from baseline in the modified Rodnan Skin Score (mRSS) at week 52. The mRSS will be calculated as a sum of all its 17 areas and will have a range from 0 (no thickening) to 51 (severe thickening in all 17 areas). A high score corresponds to worse skin thickness.
- Absolute change from baseline in St George's Respiratory Questionnaire (SGRQ) total score at week 52. Specific rules of handling of missing / inconsistent SGRQ questions are detailed in [Section 6.6](#). Please also refer to the SGRQ manual ([13](#)) for calculations of SGRQ scores. A high score corresponds to worse health.

5.2.2 (Other) Secondary endpoint(s)

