6.6.2.1.2 Saint George's Respiratory Questionnaire

As the SGRQ manual ([13](#)) allows for 25% of missing data per component (i.e., 2 questions for symptoms, 6 questions for impacts and 4 questions for activities) the rules defined in the SGRQ manual will be used to derive the SGRQ.

Additionally the responses to questions 5 and 6 will be made consistent to the extent that if the answer to question 5 is 5 (none of the time) and the answer to question 6 is non-missing (i.e., length of worst attack specified), then question 6 will be set to missing. Therefore scores will be calculated ignoring that item. In this case, the missing response to question 6 will not be included in the count of missing questions for the symptoms component.

If the patient did not receive any respiratory treatment, then Part 2 Section 5 of the SGRQ should be skipped to go directly to Section 6. In this case, based on SGRQ manual instructions, responses will be considered as zero (and thus will not be included in the count of missing questions for the impact component).

Missing questions from Part1 Section 1 ("If you ever held a job...") will be left as missing (and counted as missing).

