6.6.2.1.7 CRISS

Index score calculation:

For patients who are considered as improved over 52 weeks, in case the absolute change from baseline to week 52 in mRSS, FVC %predicted, patient global assessment, physician global assessment or HAQ-DI score is missing, then CRISS index score will be considered as missing.

In the multiple imputations step, after transformation into a binary responder variable, missing values will be imputed using the worst case (i.e. as Non-responder in all the imputations).

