6.6.2.1.8 Disease progression

The handling of missing data is summarised in the table below:

Table 6.6.2.1.8: 1 Handling of missing data for disease progression

Absolute change from baseline in FVC %predicted at 52 weeks	Change from baseline in mRSS (absolute and relative) at 52 weeks	Death	Disease progression	Missing data rule
Missing	Missing or no mRSS worsening	Alive	Yes	Worst case
Missing or no FVC worsening	Missing	Alive	Yes	Worst case
Missing or FVC worsening or no FVC worsening	Missing or mRSS worsening or no mRSS worsening	Death	Yes	None
Missing or FVC worsening or no FVC worsening	mRSS worsening	Alive	Yes	None
FVC worsening	Missing or mRSS worsening or no mRSS worsening	Alive	Yes	None
No FVC worsening	No mRSS worsening	Alive	No	None

FVC worsening means absolute decline since baseline in FVC percent predicted >10%

mRSS worsening means relative change from baseline in mRSS of >25% and absolute change from baseline of >5 points. In case baseline mRSS is 0 (and relative change can therefore not be calculated), then it will only be checked if the absolute change from baseline in mRSS is >5 points.

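### One unscored skin area makes a living patient without FVC worsening count as progressed, even when the scored areas rule out the SAP's own mRSS worsening criterion

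*SAP*

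**What the plan says.** The SAP defines the score in section 5.2.1: "The mRSS will be calculated as a sum of all its 17 areas and will have a range from 0 (no thickening) to 51". Protocol 5.2.2 describes the rating of each area as an "evaluation of patient's skin thickness rated by clinical palpation using a 0–3 scale".

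For gaps, SAP 6.6.2.1.1 has one rule: "In case of missing score for an area, mRSS total score will be missing". Nothing in the SAP prorates or bounds a partly scored total.

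Disease progression (Protocol 5.2.7) is met by FVC decline, by mRSS worsening or by death. SAP 6.6.2.1.8 states the skin limb: "mRSS worsening means relative change from baseline in mRSS of >25% and absolute change from baseline of >5 points". If baseline mRSS is 0, only the absolute limb applies.

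The relevant row of Table 6.6.2.1.8: 1, read across the columns for FVC, mRSS, vital status, progression and missing-data rule, is "Missing or no FVC worsening Missing Alive Yes Worst case". The only row that ends in No requires both components to be known and not worsened.

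Progression is a further endpoint (Protocol 5.1.3), treated as exploratory (Protocol 7.3.3) and reported with a Wilson interval and a nominal p-value (SAP 7.6.1).

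**The concern.** A worst-case rule should assign the least favourable outcome that the observed data still allow. Here it can assign an outcome that they exclude. With 16 of 17 areas scored, the possible values of the total span only 3 points. For many patients that is too narrow to reach the worsening threshold, yet they are recorded as progressed.

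The table already uses partial information in one direction: one worsened component settles progression as Yes even if the other is missing. It does not use partial information that settles the skin component as not worsened.

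What is at stake is the reported proportion with disease progression in each arm and the contrast between them.

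**Working it through.** **Inputs.** 17 areas and a total of 0 to 51 (SAP 5.2.1); 0 to 3 per area (Protocol 5.2.2); worsening if the change is above 5 points and above 25% (SAP 6.6.2.1.8); 520 randomised patients (Protocol synopsis). The gap rate per area is not in the documents and is assumed below.

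**1. The plan's own figure.** 17 × 3 = 51, which matches the stated maximum. So one area can account for at most 3 points.

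**2. Every table outcome with mRSS missing.**

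| FVC | Alive | Died |
|---|---|---|
| Missing | Yes (worst case) | Yes |
| Worsened | Yes | Yes |
| Not worsened | Yes (worst case) | Yes |

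All six combinations give progression. With FVC and mRSS both known and not worsened, a living patient is No. A patient whose FVC is missing stays Yes by worst case even if the skin is known not to have worsened. The misclassification therefore sits in one cell: alive, FVC known and not worsened, mRSS missing.

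**3. Bound on the change.** Let D be the change summed over the 16 areas scored at both visits. Let b be the baseline score of the area that is unscored at week 52.

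- Largest possible total change = D + 3 − b.
- Worsening needs a change above 5, so it is impossible when D + 3 − b ≤ 5, that is, D ≤ 2 + b.
- For b = 0, 1, 2, 3 the limit is D ≤ 2, 3, 4, 5.
- If the same area is unscored at both visits, it can contribute at most +3, so the limit is D ≤ 2.

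At D = +2 and b = 0 the largest change is 2 + 3 = 5, which is not above 5. At D = 0 it is 3. The 25% limb can only exclude worsening in further patients, so these limits are conservative.

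**4. How often the change is missing (assumed rates).** A change needs 17 areas at each of two visits, which is 34 scores. With independent gaps at rate q, P(change missing) = 1 − (1 − q)^34.

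| q per area per visit | Change missing | Of 520 |
|---|---|---|
| 0.05% | 1.7% | about 9 |
| 0.1% | 3.3% | about 17 |
| 0.5% | 15.7% | about 81 |

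These counts are ceilings. Only patients in the cell from step 2 who also meet the bound in step 3 are provably misclassified.

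**5. Effect on the proportions.** Suppose a fraction m in each arm has a missing mRSS, unrelated to outcome, and p is the proportion that would be seen with complete scores. The reported proportion is m + (1 − m)p, and the difference between arms becomes (1 − m)(p₁ − p₂). At m = 1.7%, 3.3% and 15.7% the difference keeps 98.3%, 96.7% and 84.3% of its size. For illustration, take assumed proportions of 35% and 25%, a difference of 10 points. At m = 1.7% they become 36.1% and 26.3% (9.8 points). At m = 15.7% they become 45.2% and 36.8% (8.4 points).

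**The case against.** The best defence is that this is a pre-specified, symmetric convention on an exploratory endpoint, with no evidence that single-area gaps are common. All of that stands, and it limits the point to a minor one. It does not make the classification right for a patient whose data exclude worsening.

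A second defence is consistency. SGRQ tolerates gaps because its manual "allows for 25% of missing data per component"; FACIT and HAQ-DI likewise follow cited scoring guides. No such guide is cited for mRSS gaps, and the SAP is equally strict for digital ulcers, where one unassessed finger makes the count missing (6.6.2.1.3). This is fair: the contrast with the questionnaires proves nothing. The finding rests on the bound alone.

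A reader might infer more than the documents support:

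- **That the CRISS coding is equally wrong.** A missing mRSS change makes CRISS missing, and "missing values will be imputed using the worst case (i.e. as Non-responder in all the imputations"). But absence of skin worsening does not imply CRISS response. With no change in any component, the SAP 5.2.2.1 formula gives exp(−5.54)/(1 + exp(−5.54)) = 0.004, so non-responder is almost always right. The coding is contradicted only where improvement is large. With D = −12, b = 0 and other components unchanged, the logit lies between −5.54 + 0.81 × 9 = 1.75 and −5.54 + 0.81 × 12 = 4.18, so the index is 0.85 to 0.985.
- **That the scored areas show no skin worsening at all.** They show only that the SAP threshold was not crossed; a total change of up to +5 remains possible.
- **That the confirmatory mRSS analysis is distorted by worst case.** It is an MMRM under missing at random with no such rule (SAP 6.6.2.1, 7.5.1.1). A post-baseline gap costs one visit. A baseline gap does remove the patient, but that is lost data, and SAP Table 6.2: 1 (item E3) reports missing baseline mRSS as an important protocol violation.
- **That the total should be prorated.** Areas are not interchangeable. Take a baseline total of 20 that includes one area scored 3, with no true change and that area unscored at week 52. Proration gives 17 × 17/16 = 18.06, a spurious change of −1.94, against a planned difference of 2 to 3 points (Protocol 7.7).

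**Conclusion.** The point holds as a minor one, for the disease progression endpoint only. For a living patient whose FVC is known and not worsened, one unscored area forces progression to Yes. Yet the SAP's criterion cannot be met when the scored areas changed by +2 or less (up to +5 if the unscored area was already at 3 at baseline). That result follows from the documents' own definitions and needs no assumption.

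The size does rest on assumptions: independent gaps at a rate the documents do not give. At 0.05% to 0.5% per area per visit, 1.7% to 15.7% of patients would lack a change score, and an unknown part of these would be provably misclassified. Because the rule is identical in both arms, the expected result is higher proportions in both and a somewhat smaller difference, unless incomplete scoring itself differs by arm. The primary endpoint and the testing hierarchy are unaffected.

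**What to change.** Amend SAP 6.6.2.1.8 so that the skin component is bounded before worst case is applied:

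1. Sum the change over areas scored at both visits.
2. Add 3 points for each area unscored at either visit, or 3 minus the baseline score where that score is known.
3. If the result is 5 or less, classify as no mRSS worsening and read the table with that class.
4. Otherwise, if the class is still undetermined, keep the present worst-case row.

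Section 6.6.2.1.1 can stay as it is for the MMRM and for CRISS.

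The cost is a few lines of SAP text and a short derivation from the area scores already summed for the total, settled before database lock. No imputation model is needed. The change can only turn a provably wrong Yes into No. It would also help to tabulate by arm how many week-52 totals are missing because of area-level gaps, since that shows whether the issue occurred at all.
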